5.2 Secondary Efficacy Variables

1. Actual CGI-I (Investigator-rated Clinical Global Impression – Improvement Scale) score at Visit 6
2. Change from Visit 3 to Visit 6 in CGI-S (Investigator-rated Clinical Global Impression – Severity) score
3. CHQ-PF28 at Visit 6 (Overall Health Measured by Child Health Questionnaire Parent Form 28-item)
4. PSI-4-SF at Visit 6 (Parenting Stress Index – Short Form)
5. Caregiver-completed CGI-I at Visit 6
6. SNAP-IV ADHD scores at Visit 6 (Swanson, Nolan and Pelham-IV Rating Scale for Inattention, hyperactivity-impulsivity and oppositional defiant disorder measured) in
 - Inattention

- Hyperactivity/Impulsivity
- Oppositional Defiant Disorder
- Combined subscale

CGI-I (Protocol Appendix 10.3), relative to the condition at Visit 3, will be evaluated by the caregiver and by the Investigator at Visits 4 to 6 on a 7-point scale with 1=Very much improved, 2=Much improved, 3=Minimally improved, 4=No change, 5=Minimally worse, 6=Much worse, and 7=Very much worse.

CGI-S (Protocol Appendix 10.3) will be evaluated by the Investigator at Visits 1, 3 - 6 on a 7-point scale with 1=Normal, 2=Borderline ill, 3=Mildly ill, 4=Moderately ill, 5=Markedly ill, 6=Severely ill, and 7=Extremely ill.

The Child Health Questionnaire Parent Form 28-item (**CHQ-PF28**) (Protocol Appendix 10.11) is evaluated by the primary caregiver at Visit 3 and Visit 6 for the subject's health status and health related quality of life. CHQ-PF28 items have four, five, or six response options, divided over eight multi-item scales (Physical Functioning [PF, Q2.1a–2.1c], Behavior [BE, Q5.1a-5.1c, Q5.2], Mental Health [MH, Q6.1a–6.1c], Self-Esteem [SE, Q7.1a-7.1c], General Health Perceptions [GH, Q1.1, Q8.1a-8.1c], Parental Impact - Emotional [PE, Q9.1a-9.1b], Parental Impact - Time [PT, Q9.2a-9.2b], and Family Activities [FA, Q9.3a-9.3b]) and five single item concepts (Global Health [GGH, Q1.1], Role/Social Limitations - Emotional/Behavior [REB, 3.1], Role/Social Limitations - Physical [RP, Q3.2], Bodily Pain/Discomfort [BP, Q4.1], Global Behavior [GBE, Q5.2], Family Cohesion [FC, Q9.4], and Change in Health [CH, Q8.2]). In addition, the individual scale scores will be aggregated to derive 2 summary component scores: the physical functioning and psychosocial health summary scores. Range on subscales and the overall scale is 0–100, where 0 is the worst possible health state and 100 the best possible health state. Details for item and multi-item scale scoring, calculation of standardized scores and Aggregate Physical and Psychological Summary Scores can be found in the Child Health Questionnaire (CHQ) Scoring and Interpretation Manual (HealthActCHQ).

The Parenting Stress Index – Short Form (**PSI-4-SF**) (Protocol Appendix 1.10) is a 36-item self-report measure of parenting stress at Visit 3 and Visit 6. Three subscales (Parental Distress [PD: Q1-12], Parent-Child Dysfunctional Interaction [P-CDI: Q13-24], and Difficult Child [DC: Q25-36]) consist of 12 items each. Parents use a 5-point scale to indicate the degree to which they agree with each statement. The subscale score is the sum of the respective item scores. “Total Stress” score is the sum of the 3 subscale scores. The subscale will be set to missing if 2 or more (>1) item scores in the subscale are missing. Total Stress score is set to missing if 1 or more subscale score is missing.

The **SNAP-IV** (Protocol Appendix 10.7) rating scale includes 18 ADHD and 8 oppositional defiant disorder (ODD) symptoms as specified in the DSM-IV-TR and International Statistical Classification of Diseases and Health Related Problems 10th Revision (ICD-10) Classification of Mental and Behavioral Disorders. The symptoms are scored by assigning a severity estimate for each symptom on a 4-point scale. The SNAP-IV rating is performed by the parent or legal representative at each visit. The ratings from the SNAP-IV scale are grouped into the following 4 subscales:

- ADHD-Inattention (items #1-9),
- ADHD-Hyperactivity/Impulsivity (items #10-18)
- ODD (items #19-26)
- ADHD-Combined subscale: (items #1 – 18)

Each subscale score is the average of the available item scores in the subscale. The SNAP-IV rating scale will be administered at Visit 3 and Visit 6.

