2. Actual Investigator CGI-I score at Visits 4, 5, and 6 (Table 14.2.3 and Listing 16.2.2.2)
3. Change from baseline (Visit 3) to Visits 4, 5 and 6 in Investigator CGI-S (Table 14.2.4 and Listing 16.2.2.3)
4. CHQ-PF28 Aggregate Physical and Psychological Scores will be summarized at Visit 6 (Table 14.2.5 and Listing 16.2.2.4a – Listing 16.2.2.4c)
5. PSI-4-SF will be summarized at Visit 6 (Table 14.2.6, Listing 16.2.2.5a, and 16.2.2.5b)
 - a. Parental Distress
 - b. Parent-Child Dysfunctional Interaction

- c. Difficult Child
- 6. SNAP-IV ADHD scores will be summarized at Visit 6 in (Listing 16.2.2.6a and Listing 16.2.2.6b):
 - a. Inattention ratings (Table 14.2.7.1)
 - b. Hyperactivity/Impulsivity ratings (Table 14.2.7.2)
 - c. Oppositional Defiant Disorder (Table 14.2.7.3)
 - d. Combined Scale ratings (Table 14.2.7.4)

Scores of CGI-I and CGI-S will be analyzed using a Mixed-Effects Model for Repeated Measure (MMRM). The model includes treatment, visit, and interaction between treatment and visit as fixed factors, baseline CGI-S as covariate for both CGI-I and CGI-S. The model parameters will be estimated using restricted maximum likelihood method with unstructured variance-covariance matrix and Kenward-Roger approximation to estimate denominator degrees of freedom. In case there is a convergence problem in the MMRM model with the unstructured variance covariance matrix, the first (co)variance structure which does not have convergence problem will be used for the analysis from the following ordered list: 1) Toeplitz 2) Autoregressive of order 1 3) Compound symmetry. The least squares mean of each treatment group, the difference in the least squares mean (█ mg dose minus placebo and █ mg dose minus placebo), and the 2-sided 95% CI for the difference will be obtained.

A sample SAS code is provided as follows.

```
PROC MIXED DATA=XXXX ;  
  CLASS trtp(ref="P") usubjid visit;  
  MODEL Response = base trtp visit trtp*visit / DDFM=kr ;  
  REPEATED visit / SUBJECT=usubjid(trtp) TYPE=UN ;  
  Lsmeans trtp*visit/Pdiff alpha=0.05;"  
RUN ;
```

Note: usubjid is subject ID, trtp ("P" denotes placebo treatment) is treatment variable, visit is the nominal study visit, and Response is respective endpoints.

Scores for CHQ-PF28, PSI-4-SF, and SNAP-IV will be analyzed using analysis of variance (ANOVA) at Visit 6.

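### SAP 5.2 keeps a PSI-4-SF subscale with one item missing but states only a plain sum, so that score is about one twelfth too low on average

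*SAP*

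**What the plan says.** SAP 5.2 describes three PSI-4-SF subscales that "consist of 12 items each". On responses it says: "Parents use a 5-point scale to indicate the degree to which they agree with each statement". On scoring: "The subscale score is the sum of the respective item scores". On incomplete forms: "The subscale will be set to missing if 2 or more (>1) item scores in the subscale are missing". Total Stress adds the three subscales and is missing if any one of them is missing.

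No sentence says how a subscale with exactly one missing item is calculated, and no PSI scoring manual is cited for it. The other two questionnaires in the same section are covered. For SNAP-IV, "Each subscale score is the average of the available item scores in the subscale". For CHQ-PF28, the SAP sends the reader to a named scoring manual, listed in SAP 9. Protocol 5.2.4 describes the PSI-4-SF and cites its source publication, but gives no scoring or missing-item rule.

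On analysis, SAP 7.7.7 says: "Scores for CHQ-PF28, PSI-4-SF, and SNAP-IV will be analyzed using analysis of variance (ANOVA) at Visit 6". SAP Appendix 2 plans Tables 14.2.6.1 to 14.2.6.4 as change from baseline to Visit 6, for the total and each subscale. Protocol 6.9.2 also words the endpoint as a change from Visit 3 to Visit 6.

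**The concern.** The two stated rules do not fit together. One keeps a subscale that has 11 answers; the other offers only addition. Adding 11 answers gives the unanswered item no points, so the score falls because a box was left blank and not because the parent reported less stress. Total Stress inherits the shortfall.

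The general missing-data provision does not catch this. SAP 6.4 handles missing secondary data with a mixed model, but an 11-item sum is not a missing score, and SAP 7.7.7 analyses PSI-4-SF by ANOVA in any case.

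PSI-4-SF stands in a ranked sequence (Protocol 6.9.2, SAP 7.7.7) in which a dose goes forward only if it has been significant on every endpoint so far. Avoidable noise here can therefore also cost the endpoints ranked below it. There is a practical risk too: SAP 8 requires derived datasets to be programmed twice with identical results, and two programmers could handle a one-item gap differently while both claim to follow the text.

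**Working it through.** The plan gives no figure for this point, so there is none to reproduce. The one internal count agrees: 3 subscales x 12 items = 36 items, as SAP 5.2 states.

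**Inputs from SAP 5.2**
- 12 items per subscale; score = sum; kept with one item missing.

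**Assumptions**
- Items coded 1 to 5, higher meaning more stress. The form in Protocol Appendix 10.12 prints numbers 1 to 5 only for items 22, 32 and 33. The other 33 items run from strongly agree to strongly disagree without numbers. Item 32 is printed with 1 as hardest and 5 as easiest, so some scoring key is needed. The direction is inferred from the name Total Stress.
- Share of forms with one missing item: 5 to 10%. The documents give no rate.

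**Step 1. Size for one subscale.** If the missing item equals the respondent's item mean m, the full sum is 12m and the 11-item sum is 11m. Shortfall = m/(12m) = 1/12 = 8.3%, whatever the value of m.

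| Item mean | Full sum | 11-item sum | Shortfall | 11-item sum x 12/11 |
|---|---|---|---|---|
| 2 | 24 | 22 | 2 (8.3%) | 24 |
| 3 | 36 | 33 | 3 (8.3%) | 36 |
| 4 | 48 | 44 | 4 (8.3%) | 48 |

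**Step 2. Individual spread.** One twelfth is an average. On 1-to-5 coding the loss is the value of the missing item, 1 to 5 points. As a share of the full score, the extremes are 1/(1 + 11 x 5) = 1/56 = 1.8% and 5/(5 + 11 x 1) = 5/16 = 31%. In a simulation of 200,000 forms with items drawn uniformly from 1 to 5, the mean shortfall was 8.3%, with a central 95% range of 2.6% to 15.6%.

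**Step 3. Total Stress.** One missing item among 36 costs about 1/36 = 2.8%.

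**Step 4. Arm mean at Visit 6.** If a fraction f of forms has one missing item in a subscale, its mean falls by f x m. At m = 3: 0.05 x 3 = 0.15 points; 0.10 x 3 = 0.30 points.

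**Step 5. Treatment comparison.** Equal fractions in both arms cancel, at equal item means. If one arm had 10% and the other 5%, the difference in means would shift by (0.10 - 0.05) x 3 = 0.15 points.

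**Step 6. Which visit matters.** The ANOVA in SAP 7.7.7 is at Visit 6, so a gap at Visit 6 enters it. A gap at Visit 3 does not; it affects the change columns in Tables 14.2.6.1 to 14.2.6.4, where it looks like worsening.

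**The case against.** The strongest reply is that the SAP leaves the one-item case open and does not decide it wrongly. It never says to add up whatever is available or to count a blank as 0, and SAP 4 leaves definitions of derived variables to dataset specifications that are not among these documents. A reader might infer that the plan instructs zero scoring; the text does not go that far. What remains is that addition is the only operation stated, so a literal application gives the low score, and nothing in either document prevents it.

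Second, the figures in points and the reading as lower stress depend on a scoring key that is not printed. That stands, and both are treated as assumptions here. The average of one twelfth does not need the 1-to-5 coding.

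Third, the instrument may have its own missing-item rule, which cannot be checked from these documents. That also stands, and the fix allows for it.

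Fourth, the practical effect is small. The form tells parents to answer every statement, and no rate of missing items is given. This limits the importance of the point but does not make the scoring right.

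**Conclusion.** The point holds as a minor scoring defect in a ranked secondary endpoint. Applied as written, SAP 5.2 yields a subscale that is about 1/12 (8.3%) too low on average whenever exactly one item is missing: about 3 of 36 points at an item mean of 3, under the assumed coding. If 5 to 10% of forms were affected, an arm mean would move by about 0.15 to 0.30 points, mostly as noise.

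Three stronger readings are tempting, and the documents do not support them:
- *The comparison with placebo is biased.* This needs one-item missingness to differ between arms, and nothing in the documents suggests that it does.
- *A gap at Visit 3 distorts the test.* The SAP analyses the score at Visit 6, and it supersedes the protocol's methods (SAP 1). A Visit 3 gap would matter to the test only if change from baseline were analysed.
- *Total Stress moves by 3 to 15 points.* That takes one missing item in all three subscales of the same form. Total Stress is also not among the PSI-4-SF components listed in SAP 7.7.7, which names only the three subscales.

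**What to change.** Add one sentence to SAP 5.2: when exactly one of the 12 items is missing, the subscale is the sum of the 11 available items x 12/11. If the instrument has a published missing-item rule, cite and apply that instead, as the SAP already does for CHQ-PF28. Keep the rule that two or more missing items make the subscale missing, and calculate Total Stress from the corrected subscales. State the item coding and the direction of the score in the same place.

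The cost is one sentence on scoring and one line of code, settled before database lock. Data collection, sample size and trial conduct do not change.

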5.3 Pharmacokinetic Variables

Analysis of pharmacokinetic variables will not be covered in this SAP.

5.4 Safety Variables

5.4.1 Medical History and Adverse Events (AEs)

AEs that occur on/after signing ICF will be recorded on the AE CRF. Medical history and AEs will be coded for preferred term (PT) and system organ class (SOC) using Medical Dictionary for Regulatory Activities (MedDRA) version 18.1. AEs are evaluated by the investigators for seriousness, relationship, and severity.

5.4.2 Prior, Concomitant, and Prohibited Medications

Prior medications and concomitant medications will be extracted from the Prior/Concomitant Medication CRF. Medications taken prior to Study Day 1 will be considered as prior medications and medications taken on or after Study Day 1 will be considered as concomitant medications. Prior and concomitant medications will be coded using WHO Drug Dictionary (WHODD) version 1 June, 2015 for PT and Anatomical Therapeutic Chemistry (ATC) classification.

Prohibited medications include, but are not limited to,

- α_2 - adrenergic agonists (e.g. clonidine and guanfacine) used for any other reason except for monotherapy treatment for ADHD

- Anti-psychotics including aripiprazole, risperidone, quetiapine, and ziprasidone
- Anticonvulsants including carbamazepine and valproic acid, antidepressants, mood stabilizers including lithium, benzodiazepines, cholinesterase inhibitors or any drug known to inhibit CYP2D6 activity
- Herbal supplements

5.4.3 *Clinical Laboratory Tests (Hematology, Chemistry, and Urinalysis)*

Laboratory tests will be converted to follow the International System (SI) units. Laboratory tests will be collected at Visits 1, 3, 6, and 7. The tests include hematology, serum chemistry and urinalysis panels. Laboratory values will be categorized according to the appropriate laboratory reference ranges.

5.4.4 *Vital Signs, Height and Weight*

Vital signs include body temperature, heart rate, respiratory rate, systolic blood pressure, and diastolic blood pressure. They will be collected at Visits 1 and 7. Subject height, weight, and BMI will be collected at Visits 1 and 3 – 7.

5.4.5 *12-Lead ECG*

The following ECG variables will be collected at Visits 1, 4, and 6: HR (heart rate), PR (respiratory rate), QRS interval, QT interval, and QTcF (QT interval corrected using the Fridericia's method).

5.4.6 *Physical Examinations*

Physical examinations will be conducted at Visit 1 and Visit 6. Clinically significant findings will be reported as adverse events.

5.4.7 *Columbia Suicide Severity Rating Scale (C-SSRS)*

The C-SSRS (Protocol Appendix 10.6) is a questionnaire assessing suicidal ideation and behavior at baseline and since last visit. This assessment will be conducted at Visits 1, and 3 – 7. The following outcomes are C-SSRS categories and have binary responses (yes/no).

Category 1 – Wish to be dead

Category 2 – Non-specific Active Suicidal Thoughts

Category 3 – Active Suicidal Ideation with Any Methods (Not Plan) without Intent to Act

Category 4 – Active Suicidal Ideation with Some Intent to Act, without Specific Plan

Category 5 – Active Suicidal Ideation with Specific Plan and Intent

Category 6 – Preparatory Acts or Behavior

- Category 7 – Aborted Attempt
- Category 8 – Interrupted Attempt
- Category 9 – Actual Attempt (non-fatal)
- Category 10 – Completed Suicide

Three composite binary endpoints and one severity score are derived from the above categories.

Suicidal ideation: A “yes” answer at any time during treatment to any one of the five suicidal ideation questions (Categories 1-5) on the C-SSRS.

Suicidal behavior: A “yes” answer at any time during treatment to any one of the five suicidal behavior questions (Categories 6-10) on the C-SSRS.

Suicidal ideation or behavior: A “yes” answer at any time during treatment to any one of the ten suicidal ideation and behavior questions (Categories 1-10) on the C-SSRS.

Suicidal Ideation score: The maximum suicidal ideation category (1-5 on the C-SSRS) present at the assessment. Assign a score of 0 if no ideation is present.

5.4.8 *Infrequent Behaviors Checklist*

The infrequent behaviors checklist is a checklist of 15 behaviors that (along with the 15 IA Diary behaviors) were qualitatively linked to IA during the development of the IA diary. These behaviors include teasing, spitting, biting, weapons, ripping, breaking, vandalizing, destroying, fire setting, hitting animal, kicking self, kicking animal, severe injury self, severe injury others, severe injury animal. Caregivers will be asked which, if any, of these behaviors have been observed since the patient’s last visit. This assessment will be administered at Visits 3 – 6 by the site coordinator.

5.4.9 *Extrapyramidal symptoms (EPS) scales*

The EPS symptom and neuroleptic malignant syndrome will be evaluated using the Simpson-Angus scale (Protocol Appendix 10.8), the Barnes Akathisia scale (Protocol Appendix 10.9), and the Abnormal Involuntary Movement scale (AIMS) (Protocol Appendix 10.10). The Simpson-Angus scale is a 10-item rating scale, consisting of 1 item measuring gait, 6 items measuring rigidity, and 3 items measuring glabella tap, tremor and salivation. The Barnes Akathisia scale is a rating scale for drug-induced akathisia. It includes Objective Akathisia, Subjective Awareness of Restlessness, Subjective Distress Related to Restlessness, and Global Clinical Assessment of Akathisia subscales. Additionally, total score will be calculated by summing up the Objective and two Subjective scale scores (Barnes 1989). The objective and two subjective symptoms are rated on a 4-point scale ranging from 0 to 3. The global clinical assessment is rated on a 5-point scale ranging from 0 to 4. The AIMS test is a rating scale used to measure tardive dyskinesia (Munetz

1988). It includes 12 items to rate involuntary movements of various areas of the subject's body. These assessments will be administered at Visit 3 and all subsequent visits.

6 STATISTICAL METHODS

6.1 *General Methodology*

All statistical analyses will be conducted using SAS Version 9.4 or later on the Microsoft® Windows Operating System.

All tabulations of analysis results will include summaries for the three treatment groups: SPN810 █ mg, SPN810 █ mg and placebo.

Continuous data will be summarized using n (number of subjects with non-missing observations), mean, median, standard deviation (SD), minimum value, and maximum value. Categorical data will be summarized using the frequency count and percentage (n, %) of subjects in each category. Number of subjects with non-missing values or number of subjects with missing values (e.g., Not Done) will be presented, where appropriate. Subjects with missing values will not contribute to the denominator of percentage calculations. Counts of zero in any category will be presented without percentage.

Treatment differences will be evaluated as SPN-810 dose minus placebo. Unless otherwise specified, all statistical hypothesis tests will be 2-sided with a significance level of $\alpha=0.05$. All confidence interval will be calculated 2-sided from the unadjusted 5% significance level. P-values will be reported to 4 decimal places. P-values <0.0001 will be presented as " <0.0001 ". Similarly, p-values >0.9999 will be presented as " >0.9999 ".

The precision rules for the presentation of summary statistics will be:

- Sample size (n, N) and number of missing responses (if displayed) – Integer
- Mean, median, percentiles, and confidence interval – One additional decimal place than reported/collected
- Standard deviation – Two additional decimal places than reported/collected
- Minimum, maximum – Same number of decimal places as reported/collected
- Ratios – two decimal places
- Percentages – one decimal place generally, or two decimal places for $<0.1\%$

The data summaries will be accompanied by individual subject data listings. All data available from diary, eCRF, and external transfer (labs) will be listed and will include relevant and pertinent subject information, e.g., treatment, center, age/gender/race, and study day. The listings will be

sorted in the order of treatment group, unique subject ID, and assessment date/time and assessment name. The unique subject ID consists of 3-digit study number followed by []-digit site number and []-digit subject number separated by hyphen (e.g., []).

For each summary table, a supporting listing will be identified in the footnote.

Dates will be presented in the ISO-8601 format YYYY-MM-DD. Times will be displayed in 24-hour clock format. Numbering for tables, figures and listings will follow ICH E3 Guidelines.

Alternative methods of analysis of the data may be considered prior to un-blinding when some of the assumptions underlying the proposed analyses not be met. However, the reason for any departure from the planned approach and methods will be fully documented as an amendment to the SAP or in the clinical study report.

6.2 Visit Window and Unscheduled Assessments

There is no visit window for the by visit analysis. Data will be analyzed according to the visit they are associated with. Data collected at unscheduled time points will not be summarized at the unscheduled time points. However, the unscheduled data will be used for analysis if data are missing at the next scheduled visit due to early termination.

6.3 Adjustment for Covariates

An exploratory analysis of the primary efficacy endpoint will be performed using a randomization-based approach (Dmitrienko and Koch 2017). This analysis will include age (categorical and continuous), gender, pooled site and baseline IA adjusted to 7 days as covariates.

6.4 Handling of Dropouts, Missing Data, and Data Discrepancies

For the primary analysis of the primary efficacy endpoint, the frequency of IA behaviors during the treatment (titration + maintenance) period will be calculated over the number of days with non-missing IA diary data in the treatment period. No explicit imputation of missing data will be used, but this approach is implicitly equivalent to using the frequency of IA behaviors during the days with non-missing IA diary data to impute the frequency for days after study discontinuation or days with missing IA diary data. In addition to this implicit imputation, multiple imputations under the assumption of missing at random (MAR) and missing not at random (MNAR) will be used for handling missing data for sensitivity analysis. Details of imputation methods are specified in Section [7.7.2](#).

For analysis of frequency of IA behaviors during the treatment period (titration or maintenance), the following methods will be followed.

- 1) If subjects discontinued the study during the maintenance period, their maintenance period will be counted from Visit 5 (exclusive) through the date of last dose as documented on the End of Study eCRF page (inclusive). If the date of last dose is not collected, it will be imputed by the subjects' last visit for the study.
- 2) If subjects have ≥ 7 daily diaries in the maintenance period, their maintenance IA frequencies will be based on maintenance daily diaries.
- 3) If subjects have <7 daily diaries in the maintenance period, their maintenance IA frequencies will be calculated pooling the titration period diaries with the maintenance period diaries.
- 4) If subjects do not have any maintenance diaries, their maintenance IA frequencies will be entirely derived from the titration period diaries.

Missing data for secondary efficacy endpoints will be handled by using the Mixed Model for Repeated Measures method, which is implemented via SAS® PROC MIXED procedure. MMRM assumes data are “Missing At Random (MAR)”. That is, the probability that an observation is missing may depend on the observed values but not the missing values in the previously scheduled visits.

AEs with incomplete information for start or stop dates (i.e., either day or month is missing) will be considered treatment-emergent (TEAE) unless the partial start date or the stop date confirms the AE started or ended prior to Study Day 1 (e.g., the day of the AE start date is unknown but the month and year indicate that the AE starts prior to Study Day 1). AEs with missing relationship to study drug will be included in the “Related” category for the summary tables (Section 7.8.1). AEs with missing severity will not be included in the summary table but will be footnoted.

When there is incomplete information regarding dosing dates for prior and concomitant medication, the medication will be considered as a concomitant medication unless it contradicts with the stop date. For example, a medication will be considered a prior medication if the month and year of the end date indicates a date before Study Day 1 even though the start date could be missing.

6.5 *Interim Analysis and Adaptive Design*

The sample size estimation described in Section 3.5 is based on the effect size assumptions from the Phase 2 data in which the primary endpoint was the change from baseline to endpoint in R-MOAS ratings. However, the primary endpoint for this study is percent change in the frequency of IA incidence per 7 days in the treatment period (PCH_T) relative to the Baseline period in the ITT population. Hence, there is uncertainty as to what magnitude of alternative hypothesis

treatment difference and between-subject variability is appropriate for the sample size calculation. To this end, a single interim analysis is planned after approximately 50% of subjects complete the study for the purpose of the Stage 2 sample size adjustment.

6.5.1 *Objective*

The primary objective of this Interim Analysis is to re-evaluate the pre-specified power and sample size to consider sample size adjustment using adaptive statistical methods.

6.5.2 *Responsible Party*

This interim analysis will be performed by an independent unblinded statistician who is not affiliated to the trial sponsor, trial management, data cleaning, and analysis.

The Senior Director of Biostatistics and Executive VP and Chief Medical Officer for Clinical Developmen at Supernus (sponsor) will receive recommendation letter from the independent unblinded statistician. They will make the final decision for the sample size adjustment.

6.5.3 *Confidentiality*

The independent statistician will sign the confidentiality agreement. He/she will not reveal any unblinded data/information to any persons within his/her own organization or to the sponsor, with the exception of sending recommendation as described in Section [6.5.8](#) below.

6.5.4 *Scope of Data Being Analyzed*

Primary efficacy endpoint – percent change in the frequency of impulsive aggression behaviors per 7 days in the treatment (PCH_T) period relative to Baseline period in the ITT population. The primary efficacy analysis will be performed using the Wilcoxon rank-sum test to compare the medians of each of the two doses of SPN-810 (█ mg and █ mg) with the median of the Placebo.

6.5.5 *Procedures for Interim Analysis*

- a. Cutoff dates for collection of diary data for efficacy analysis is established based on an estimated target date of 50% of the randomized subjects completing/discontinuing the study.
- b. All data received by the cutoff date will be validated, queries generated and resolved or pending queries documented.
- c. A snapshot of the diary data will be taken and used for the interim analysis.
- d. From the data obtained at the time of the interim analysis, the independent statistician will calculate

- The Conditional Power (CP_L) associated with SPN-810 [] mg/day
- The Conditional Power (CP_H) associated with SPN-810 [] mg/day

Using the formula derived from Chang (2008a), Hintze (2013), (Chen, 2004), and Jennison and Turnbull (2005),

$$CP(n_2, \alpha_2, p_1 | \delta, \sigma) = 1 - \Phi \left(\frac{1}{\sqrt{w_2}} [Z_{1-\alpha_2} - \sqrt{w_1} Z_{1-p_1}] - \frac{\delta}{\sigma} \sqrt{\frac{n_2}{2}} \right)$$

$$1 - \Phi \left(\frac{1}{\sqrt{w_2}} [Z_{1-\alpha_2} - \sqrt{w_1} Z_{1-p_1}] - Z_{1-p_1} \sqrt{\frac{n_2}{n_1}} \right),$$

where δ/σ is the expected effect size (standardized treatment difference from placebo), $w_1 = \frac{n_1}{n_1+n_2}$, $w_2 = \frac{n_2}{n_1+n_2}$ are the weights for the average of the Stage 1 and Stage 2 test statistic, n_1 is the sample size at stage 1, n_2 is the planned sample size per group at Stage 2 (increment from interim to final), $\alpha_2 = 0.025$ is the one-sided Type-I error for the final analysis, and Z_{1-p_1} is the Wilcoxon Rank Sum Z statistic with continuity correction at the interim analysis (Stage 1). When the interim analysis is conducted with 50% subjects have completed the study, $w_1 = w_2 = 1/2$. For the sample size re-estimation, Stage 2 data are assumed to follow the trend observed in Stage 1. Hence, the effect size is calculated as $\frac{\delta}{\sigma} = Z_{1-p_1} \sqrt{\frac{2}{n_1}}$. (Chang 2008b).

